8.2 SAFETY ASSESSMENTS

Planned timepoints for all safety assessments are provided in the SoA (Section 1.3).

Safety assessments will consist of monitoring and recording AEs, including SAEs and non-serious AEs of special interest (NSAESI); measurement of protocol-specified safety laboratory assessments; measurement of protocol-specified vital signs, ECGs; and other protocol-specified tests that are deemed critical to the safety evaluation of the study.

8.2.1 Physical Examinations

A complete physical examination will include, at a minimum, assessments of the cardiovascular, respiratory, gastrointestinal, dermatological, neurological, and musculoskeletal systems; in addition to head; eyes; ears; nose; throat; neck; and lymph node systems. Height and weight will also be measured and recorded. Further examination of other body systems may be performed at the Investigator's discretion.

An abbreviated physical examination will include, at a minimum, assessments of the cardiovascular, respiratory, gastrointestinal, dermatological, and neurological systems; and measurement of body weight.

A complete or abbreviated physical examination will be performed at the timepoints specified in the SoA (Section 1.3) by trained medical personnel at the study center. Attention should be paid to signs and symptoms suggestive of type 3 hypersensitivity reactions.

The BMI will be calculated. Height will be recorded at screening only. Body weight will be recorded at screening and at all subsequent physical examinations and as clinically indicated.

Any abnormality identified at baseline should be recorded on the General Medical History and Baseline Conditions eCRF.

Changes from baseline abnormalities should be recorded in participant's notes. New or worsened clinically significant abnormalities should be recorded as AEs on the Adverse Event eCRF.

8.2.2 Vital Signs

BP, pulse rate, body temperature (*forehead*, tympanic or oral) and respiratory rate will be assessed at the timepoints specified in the SoA (Section 1.3).

BP and pulse measurements will be assessed in a supine position with a completely automated device. Manual techniques will be used only if an automated device is not available. When possible, the same arm should be used for all BP measurements.

BP and pulse measurements should be preceded by at least 5 minutes of rest for the participant in a quiet setting without distractions (e.g., television, cell phones).

Three readings of BP and pulse will be taken. The first reading should be rejected. The second and third readings should be averaged to give the measurement to be recorded in the eCRF.

Single measurements of the other vital signs will be taken before blood collection for laboratory tests but after ECG collection when scheduled at the same timepoint.

The timings of assessments may be amended or the number of assessments increased during study conduct on the basis of emerging data in order to allow for optimal characterization of the effect profile.

8.2.3 Electrocardiograms

Triplicate 12-lead ECG will be obtained as outlined in the SoA (see Section 1.3) using an ECG machine. Measurements of PR, QRS complex (QRS), QT, and QTc intervals may be performed by the instrument or calculated using an external tool.

At each timepoint at which triplicate ECGs are required, three individual ECG tracings should be obtained as closely as possible in succession but no more than 5 minutes apart. The full set of triplicates should be completed in less than 10 minutes.

To minimize variability, it is important that participants be in a resting position for ≥ 10 minutes prior to each ECG evaluation. Body position should be consistently maintained for each ECG evaluation to prevent changes in heart rate. Environmental distractions (e.g., television, radio, conversation) should be avoided during the pre-ECG resting period and during ECG recording. ECGs should be performed prior to any scheduled vital sign measurements and blood draws. In some cases, it may be

appropriate to repeat abnormal ECGs to rule out improper lead placement as contributing to the ECG abnormality.

For safety monitoring purposes, the Investigator or designee must review, sign, and date all ECG tracings. Paper or electronic copies will be kept as part of the participant's permanent study file at the site. If considered appropriate by Roche, ECGs may be analyzed retrospectively at a central laboratory.

ECG characteristics (including heart rate, QRS duration, and PR, and QT intervals) will be recorded on the eCRF. QTcF (Fridericia's correction) and RR will be calculated and recorded on the eCRF. Changes in T-wave and U-wave morphology and overall ECG interpretation will be documented on the eCRF. T-wave information will be captured as normal or abnormal, U-wave information will be captured in two categories: absent/normal or abnormal.

8.2.4 Clinical Safety Laboratory Assessments

Normal ranges for the study laboratory parameters must be supplied to the Sponsor before the study starts. A list of clinical laboratory tests to be performed is provided in [Appendix 4](#) and these assessments must be conducted in accordance with the separate laboratory manual and the SoA (Section 1.3).

The Investigator must review the laboratory report, document this review, and record any clinically relevant changes occurring during the study in the AE section of the CRF. The laboratory reports must be filed with the source documents. Clinically significant abnormal laboratory findings are those which are not associated with the underlying disease, unless judged by the Investigator to be more severe than expected for the participant's condition.

- In the event of unexplained abnormal clinically significant laboratory test values, the tests should be repeated immediately and followed up until they have returned to the normal range and/or an adequate explanation of the abnormality is found.
- If such values do not return to normal/baseline within a period of time judged reasonable by the Investigator, the etiology should be identified and the Sponsor notified.
- If laboratory values from non-protocol-specified laboratory assessments performed at the local laboratory require a change in participant management or are considered clinically significant by the Investigator (e.g., SAE or AE or dose-modification) then, the results must be recorded in the CRF/Clinical Trial Adverse Event/Special Situations Form.

Results of clinical laboratory testing will be recorded on the eCRF or be received as electronically produced laboratory reports submitted directly from the local or central laboratory.

Additional blood or urine samples may be taken at the discretion of the Investigator if the results of any test fall outside the reference ranges, or clinical symptoms necessitate additional testing to monitor participant safety.

Where the clinical significance of abnormal laboratory results at screening is considered uncertain, screening laboratory tests may be repeated before randomization to confirm eligibility.

If there is an alternative explanation for a positive urine or blood test for drugs of abuse, e.g., previous occasional intake of a medication or food containing for example, codeine, benzodiazepines or opiates, the test could be repeated to confirm washout.

Samples collected before dosing or from participants on placebo are to be taken as a precautionary measure and may not be analyzed in the first instance.

8.2.5 Safety Biomarker Assessments

Quantitative changes in T_{reg} , T_{eff} , NK cells, and eosinophils will be evaluated as exploratory safety biomarkers. Cytokines, including but not limited to, IL-6, IL-8, TNF- α , or IL-1 β may be measured as exploratory safety biomarkers ad hoc in participants experiencing symptoms associated with IRRs. These assessments are described in Section 8.7.

Total IgE, tryptase, safety cytokines, and further exploratory safety biomarkers may be tested in case of participants experiencing signs and symptoms associated with IRRs (IRR samples; see Section 1.3). This includes hypersensitivity reactions.

8.2.6 Local Pain and Skin Reactivity Assessments

Local pain and ISRs (e.g., burning, bleeding, itching, bruising, redness, hive formation, or other) may be assessed at any time in the study.

Participants will be asked an additional set of questions via an ISR questionnaire (see Appendix 6) to capture self-reported experiences of ISRs.

8.2.7 Medical History and Demographic Data

Medical history includes clinically significant diseases (including AIH and other AIDs), surgeries, cancer history (including prior cancer therapies and procedures), reproductive status, smoking history, use of alcohol and drugs of abuse and all medications (e.g., prescription drugs, OTC drugs, herbal or homeopathic remedies, nutritional supplements) used by the participant within 14 days prior to the screening visit.

Demographic data will include age, sex, and self-reported race/ethnicity.

8.3 ADVERSE EVENTS AND SERIOUS ADVERSE EVENTS

The definitions of an AE or SAE can be found in [Appendix 2](#). The NSAESI are discussed in Section [8.3.6](#).

The Investigator and any qualified designees are responsible for ensuring that all AEs (including assessment of seriousness, severity, and causality; see [Appendix 2](#)) are recorded on the Adverse Event eCRF and reported to the Sponsor in accordance with instructions provided in this section and in [Appendix 2](#).

Procedures used for recording AEs are provided in [Appendix 3](#).

8.3.1 Time Period and Frequency for Collecting Adverse Event and Serious Adverse Event Information

The method of recording, evaluating, and assessing causality of AEs and SAEs and the procedures for completing and transmitting SAE reports are provided in [Appendix 2](#).

Investigators will seek information on AEs at each participant's contact. All AEs, whether reported by the participant or noted by study personnel, will be recorded in the participant's medical record and on the Adverse Event eCRF as detailed below.

After informed consent has been obtained **but prior to initiation of study treatment**, only SAEs caused by a protocol-mandated intervention should be reported (e.g., SAEs related to invasive procedures such as biopsies). Any other AE should not be reported.

After initiation of study treatment, all AEs, regardless of relationship to study treatment, will be reported until the follow-up visit, which is scheduled 28 days after last dose of study treatment.

Post-study AEs and SAEs: The Investigator is not required to actively monitor participants for AEs after the end of the AE reporting period (e.g., follow-up visit).

However, if the Investigator learns of any SAE (including a death) or other AEs of concern that are believed to be related to prior treatment with study treatment, at any time after a participant has been discharged from the study, and the Investigator considers the event to be reasonably related to the study treatment or study participation, the Investigator must promptly notify the Sponsor. For the procedure of reporting, see [Appendix 2](#).

8.3.2 Method of Detecting Adverse Events and Serious Adverse Events

Care will be taken not to introduce bias when detecting AEs and/or SAEs. Open-ended and non-leading verbal questioning of the participant is the preferred method to inquire about AE occurrence.

A consistent methodology of non-directive questioning should be adopted for eliciting AE information at all participant evaluation time-points.

8.3.3 Follow-Up of Adverse Events and Serious Adverse Events

8.3.3.1 Investigator Follow-Up

The Investigator should follow up each AE until the event has resolved to baseline grade or better, the event is assessed as stable by the Investigator, the event is otherwise explained, the participant is lost to follow-up (Section 7.3), or the participant withdraws consent. Every effort should be made to follow all SAEs considered to be related to study treatment or study-related procedures until a final outcome can be reported.

During the study period, resolution of AEs (with dates) should be documented on the Adverse Event eCRF and in the participant's medical record to facilitate source data verification. If, after follow-up, return to baseline status or stabilization cannot be established, an explanation should be recorded on the Adverse Event eCRF.

All pregnancies reported during the study should be followed until pregnancy outcome and reported according to the instructions provided in Section 8.3.5.

8.3.3.2 Sponsor Follow-Up

For SAEs, NSAESIs, and pregnancies, the Sponsor or a designee may follow up by telephone, fax, electronic mail, and/or a monitoring visit to obtain additional event details and outcome information (e.g., from hospital discharge summaries, consultant reports, autopsy reports) in order to perform an independent medical assessment of the reported event.

8.3.4 Regulatory Reporting Requirements for Serious Adverse Events

Prompt notification by the Investigator to the Sponsor of a SAE is essential so that legal obligations and ethical responsibilities towards the safety of participants and the safety of a study treatment under clinical investigation are met.

The Sponsor has a legal responsibility to notify both the local regulatory authority and other regulatory agencies about the safety of a study treatment under clinical investigation. The Sponsor will comply with country-specific regulatory requirements relating to safety reporting to the regulatory authority, Institutional Review Boards (IRB)/Independent Ethics Committees (IEC), and Investigators.

Investigator safety reports must be prepared for suspected unexpected serious adverse reactions according to local regulatory requirements and Sponsor policy and forwarded to Investigators as necessary.

An Investigator who receives an Investigator safety report describing a SAE or other specific safety information (e.g., summary or listing of SAEs) from the Sponsor will

review and then, file it along with the IB and will notify the IRB/IEC, if appropriate according to local requirements.

For immediate and expedited reporting requirements from Investigator to Sponsor and from Sponsor to Health Authority, Investigators, IRB and IEC; see [Appendix 2](#).

8.3.4.1 Emergency Medical Contacts

To ensure the safety of study participants, access to the Medical Monitors is available 24 hours a day, 7 days a week. Details will be available separately.

8.3.5 Pregnancy

WOCBP will be instructed to immediately inform the Investigator if they become pregnant during the study or within 28 days after the final dose of study treatment.

If a pregnancy is reported, the Investigator should inform the Sponsor within 24 hours of learning of the pregnancy and should follow the pregnancy reporting process as detailed in [Appendix 5](#).

Abnormal pregnancy outcomes (e.g., spontaneous abortion, fetal death, stillbirth, congenital anomalies, ectopic pregnancy) are considered SAEs ([Appendix 5](#)).

8.3.6 Non-Serious Adverse Events of Special Interest

NSAESIs are required to be reported by the Investigator to the Sponsor immediately (i.e., no more than 24 hours after learning of the event; see [Appendix 2](#) for reporting instructions).

NSAESIs for this study include the following:

- Cases of an elevated ALT or AST in combination with either an elevated bilirubin or clinical jaundice, as defined in [Appendix 3](#).
- Suspected transmission of an infectious agent by the study treatment, as defined below:

Any organism, virus, or infectious particle (e.g., prion protein transmitting transmissible spongiform encephalopathy), pathogenic or non-pathogenic, is considered an infectious agent. A transmission of an infectious agent may be suspected from clinical symptoms or laboratory findings that indicate an infection in a participant exposed to a medicinal product. This term applies only when a contamination of the study treatment is suspected.

- NCI CTCAE (v5.0) \geq Grade 2 IRRs and any hypersensitivity.

8.3.7 Management of Specific Adverse Events

Treatment of AEs will be considered on a case-by-case basis according to local standard of care.

IRRs have been reported with the first or second infusion/injection (e.g., of biologic therapies) and tend to be dose-related. Such reactions typically occur during, shortly after or within 24 hours after study treatment administration.

“IRR” is a basket term including other terms such as anaphylaxis, anaphylactoid reactions, complement activation-related pseudoallergy, and cytokine release syndrome. Combinations of IRR types may occur in the same patient ([Doesseger et al. 2015](#)). A localized ISR is not by itself considered an IRR.

IRR symptoms may be indistinguishable from an anaphylaxis type 1 hypersensitivity reaction (i.e., flushing, rash, respiratory difficulty, hypotension, tachycardia); however, hypersensitivity reactions (IgE-mediated) generally do not occur with the first exposure to a compound (e.g., biologic therapy).

The participant should be monitored until complete resolution of the symptoms and treated as clinically indicated.

An IRR blood sample will be taken in all participants at baseline (Day 1 at pre-dose) (see Section 1.3). In case a Grade ≥ 2 IRR occurs, unscheduled PK and IRR samples will be collected and analyzed. The baseline samples of all participants may be analyzed as appropriate.

In case of signs/symptoms of IRRs in a given arm, IRR risk mitigation steps may be implemented in the remaining participants of the dose level. In order to reduce the occurrence and potential impact of IRRs, pre-medication (e.g., anti-histamine) may be applied after discussion between the Sponsor Clinical Pharmacologist, the Investigator, the safety science leader, and the Medical Monitor(s).

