6.3.2 Blinding

Interim analyses will be conducted by a group independent of the study team and decisions flowing from the results of the interim analyses will be communicated in a blinded fashion.

PK/PD data can be received and cleaned on an ongoing basis. The data will be handled and cleaned in a restricted area which is not accessible by any blinded study management team member.

If unblinding is necessary for participant management (in the case of an SAE), the Investigator will be able to break the treatment code by contacting the IxRS. Treatment codes should not be broken except in emergency situations. If the Investigator wishes to know the identity of the study treatment for any other reason, he/she should contact the Medical Monitor directly. The Investigator should document and provide an explanation for any premature unblinding (e.g., accidental unblinding, unblinding due to a SAE).

The randomization schedule will not be made available to any member of the core study team. The randomization schedule may be made available to members of the extended study team on the basis of operational need. Reasons for providing access to the randomization list include, but is not limited to, support for the functions of the IMC and PK. The names and responsibilities of all those to whom the randomization schedule is released will be documented in the eTMF along with the date of release. As per Health Authority reporting requirements, the Sponsor will break the treatment code for all unexpected SAEs (see Section 8.3.4) that are considered by the Investigator to be related to study treatment.

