8.5 PHARMACOKINETICS

Mandatory blood samples to evaluate serum concentrations of RO7049665 will be collected at on-treatment visits as specified in the SoA (see Section 1.3). The date and time of each sample collection will be recorded in the eCRF. Serum concentrations of RO7049665 will be measured by specific and validated enzyme-linked immunosorbent assay methods.

During the course of the study, PK sampling timepoints may be modified on the basis of emerging data to ensure the PK of RO7049665 can be adequately characterized. Additional PK samples will be taken at the time of treatment discontinuation, if the participant experiences an injection-related AE (such as an IRR).

- Placebo-treated participants may not be analyzed in the first instance, but retained for subsequent analysis if appropriate.
- If required, remaining PK samples, or any remaining volume of blood samples, may also be used for assay development/validation experiments and ADA characterization.

The PK samples will be destroyed 5 years after the date of final clinical study report (CSR). Details on sampling procedures, sample storage, and shipment are given in the sample documentation.

Genetic analyses will not be performed on these samples unless consent for this was included in the informed consent. Participant confidentiality will be maintained.

Drug concentration information that may unblind the study, will not be reported to investigative sites or blinded personnel until the study has been unblinded.

For participants who consent to RBR, leftover samples will be transferred to RBR (see Section 8.9).

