Pregnancy Test	
 All women of childbearing potential (including those who have had a tubal occlusion/ligation) will have a blood pregnancy test at screening. Urine pregnancy tests will be performed at specified subsequent visits. If a urine pregnancy test is positive, it must be confirmed by a blood pregnancy test.
Anti-Drug Antibodies	
 As specified
Urinalysis	
 Specific gravity Dipstick: pH, glucose, protein, blood. If there is a clinically significant positive result (confirmed by a positive repeated sample), urine will be sent to the local laboratory for microscopy and culture. If there is an explanation for the positive dipstick results (e.g., menses), it should be recorded and there is no need to perform microscopy and culture. Microscopic examination (red blood cells [RBCs], white blood cells [WBCs], casts, crystals, epithelial cells, bacteria), if blood or protein is abnormal.
Other Screening Tests	
 Urine drug screen (to include at minimum: amphetamines, barbiturates, cocaine, opiates, codeine, and benzodiazepines). Alcohol breath test.

The results of each local test must be entered into the CRF.

Investigators must document their review of each laboratory safety report.

Laboratory/analyte results that could unblind the study, will not be reported to investigative sites or other blinded personnel until the study has been unblinded.

Additional Statistical Considerations for Clinical Laboratory Data

- **Standard Reference Ranges and Transformation of Data**

Potential analysis considerations for analyzing laboratory data includes the use of standard reference ranges and potential transformation of data for specific laboratory tests.

In this scenario, Roche standard reference ranges, rather than the reference ranges of the Investigator, can be used for specific parameters. For these parameters, the measured laboratory test result will be assessed directly using the Roche standard reference range. Certain laboratory parameters will be transformed to Roche's standard reference ranges.

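### Section 8.3.7 allows injection-related-reaction mitigation to be rolled out by dose level, and no blinding safeguard in the protocol covers that step (minor; cheap to improve)

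*Combined protocol and SAP*

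**What the plan says.** Section 8.3.7 (Management of Specific Adverse Events) sets the trigger by arm, "In case of signs/symptoms of IRRs in a given arm", and the roll-out by dose: "IRR risk mitigation steps may be implemented in the remaining participants of the dose level". It sets no minimum grade or number of reactions. A separate sentence then allows pre-medication, with antihistamine as the example, after a discussion that includes the Investigator and sponsor staff. That sentence does not mention arm or dose. The section also notes that "IRRs have been reported with the first or second infusion/injection (e.g., of biologic therapies) and tend to be dose-related".

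Several other places protect the blind:

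- Section 6.3.2 on code breaks: "Treatment codes should not be broken except in emergency situations".
- Section 6.3.2 on the schedule: "The randomization schedule will not be made available to any member of the core study team". It also requires decisions that follow from the interim analyses to be passed on in blinded form.
- Section 8.5: "Drug concentration information that may unblind the study, will not be reported to investigative sites or blinded personnel" before the study is unblinded.
- Appendix 4: "Laboratory/analyte results that could unblind the study, will not be reported to investigative sites or other blinded personnel" before the study is unblinded.

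Section 4.1.5 and Appendix 1 (Section 3.3) set up an unblinded IMC that reviews safety and efficacy data. Its communication plan is left to a charter that is not part of the documents.

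**The concern.** The dose-level rule cannot be followed without arm information. Someone must know which arm the reactions occurred in and who else is on that dose. If the measure is one that sites and participants can see, and sites know it is being applied by dose, then giving it to a participant discloses that participant's dose group.

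The trigger is plausible. Section 2.2.2.1 reports IRRs in the ongoing ulcerative colitis study of 3.5 mg and 7.5 mg. Section 8.3.7 expects IRRs to be dose-related, so 7.5 mg, the dose in the primary comparison, is the likelier target.

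Most relapses should come from centrally measured ALT and IgG against fixed thresholds (Section 8.1, Table 8). Two endpoint components depend on the Investigator:

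- Raising or restarting corticosteroids for an AIH flare counts as an event (Section 8.1; Section 3.1.3, Table 6).
- Permanent discontinuation counts as an event if related to treatment and is censored if not (Table 6). The Investigator judges whether adverse events are related (Appendix 2, Section 3.2).

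Knowledge of the arm could colour either judgement.

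**Working it through.** The plan gives no figure for this point, so the check has two parts: whether any safeguard reaches the step, and what a site could infer if the rule were used.

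**1. Does a safeguard cover it?**

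| Place | What it protects | Covers dose-level IRR mitigation? |
|---|---|---|
| 6.3.2 | Access to the randomization schedule | Not directly: it limits who holds the list, not what sites are told to do |
| 6.3.2 | Code breaks | No |
| 6.3.2 | Communication of interim-analysis decisions | No: this is a safety measure |
| 8.5 | Drug concentrations | No |
| Appendix 4 | Laboratory and analyte results | No |
| 6.5.1 | Permits IRR pre-medication for any participant | No: it permits, but does not require equal use across arms |
| 4.1.5; Appendix 1, 3.3 | Unblinded IMC with a charter | Unknown: the charter is not available |

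**2. What could be inferred?**

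Inputs: 1:1:1 allocation (Section 4.1) and 28 per arm, 84 in total (Section 9.2). Assumptions: the measure is visible, it is applied consistently to the remaining participants of the dose level, and the site knows it follows dose. The quantity is the chance that a comparable participant without the measure is on placebo, which is the placebo number divided by the number in all arms still possible.

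- No roll-out: 28/84 = 1/3.
- (a) 7.5 mg only: 28/(28 + 28) = 1/2. Those given the measure are known to be on 7.5 mg.
- (b) Both active doses: 28/28 = 1. Active and placebo are separated.
- (c) 3.5 mg only: 28/(28 + 28) = 1/2. The rest are 7.5 mg or placebo, so the primary comparison stays blinded.

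**3. How many could be exposed under (a)?**

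The ceiling is 28 − 1 = 27 in the 7.5 mg arm, leaving out the participant whose reaction triggers the roll-out. This is an upper limit, because 8.3.7 places IRRs at the first or second injection, so mitigation would mainly concern later enrollees. Table 9 estimates 31 participants in two arms at month 11.7 and 47 at month 16.3. With equal allocation:

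- Month 11.7: 31/2 = 15.5 enrolled per arm, so 28 − 15.5 = 12.5 still to enroll.
- Month 16.3: 47/2 = 23.5 enrolled per arm, so 28 − 23.5 = 4.5 still to enroll.

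These counts are illustrative only. The two dates are Table 9's interim-analysis times; the documents do not predict when IRRs would occur.

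**4. Which way could it act?**

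An Investigator who believes a participant is not on active drug might restart steroids sooner, which would favour the drug. An Investigator who knows a participant is on active drug might more readily call a discontinuation related, which adds an event and works against the drug. The documents give no frequency for either, so neither the net direction nor the size follows.

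**The case against.** The strongest case against the point has five parts.

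- **The dose-level sentence names no measure.** Antihistamine pre-medication is in a separate sentence not tied to dose, and Section 6.5.1 allows it for anyone. This stands: pre-medication marks an arm only if it is applied by dose level and sites know that. It does not make the dose-level sentence neutral.
- **Controls exist.** Blinded staff cannot act on one arm unless a schedule holder tells them, releases of the schedule are documented, and the IMC reviews safety data. This stands in part: the charter may contain a procedure. But 8.3.7 neither refers to the IMC nor says how sites are to be instructed.
- **The scope is narrow.** Grade 3 or higher IRRs stop the individual's dosing (4.1.3), and related Grade 3 hypersensitivity in more than one participant suspends study dosing (4.1.2). The rule therefore mainly concerns Grade 1–2 reactions. This stands.
- **The endpoint is largely protected and the blind is already imperfect.** ALT and IgG are central. Two of the Section 3.1.5 sensitivity analyses treat all intercurrent events as relapses or all as censored, which would help expose an effect through the judged components but would not prevent it. Injection-site reactions rose with dose in healthy volunteers, and eosinophilia was frequent in the colitis study (2.2.2.1). This limits the added risk, but is no reason to add an explicit clue.
- **Targeting a safety measure at those at risk is defensible.** It is a fair trade-off, and it is why arm-neutral use has a real, if small, cost.

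A reader might infer that 8.3.7 will unblind the trial. The documents do not support that: the step is optional, and disclosure needs reactions attributed to an arm, a visible measure, dose-level use and site awareness, all together.

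**Conclusion.** The point holds as a minor, conditional weakness. Section 8.3.7 states a rule, by arm and by dose level, that no blinding safeguard in the protocol reaches. If it were used with a visible measure known to follow dose, roll-out at 7.5 mg would identify the affected 7.5 mg participants and narrow the others to two arms. Roll-out at both doses would separate active from placebo. Roll-out at 3.5 mg alone would leave the primary comparison blinded.

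Two stronger conclusions are not supported. One is that the primary hazard ratio would be biased in the drug's favour: the two judged components could act in opposite directions, and the documents give nothing from which to size either. The other is that roll-out at 7.5 mg alone would identify the placebo arm: those without the measure could equally be on 3.5 mg.

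The conclusion assumes that the IMC charter does not already make the step arm-neutral, which cannot be checked from the documents.

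**What to change.** In Section 8.3.7, replace the dose-level sentence with wording such as:

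> *Any study-level IRR mitigation will be applied identically to participants in all three arms; individual pre-medication after a participant's own reaction remains permitted under Section 6.5.1. Where arm-level IRR data are needed for this decision, they will be reviewed by the unblinded IMC and only the arm-neutral instruction communicated to sites (Section 6.3.2). The stopping rules in Section 4.1.2 and regulatory code breaks are unaffected.*

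The last sentence is needed. Section 4.1.2 counts reactions in participants treated with RO7049665 and brings sponsor leads, the IMC and Investigators into some dosing decisions, and Section 6.3.2 provides for sponsor code breaks for unexpected related serious events. If the charter already has an arm-neutral procedure, 8.3.7 should cite it and drop the dose-level wording. Which measure to use remains a clinical decision.

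The cost is one paragraph in the next amendment and, if needed, a line in the charter. Some placebo and other-dose participants may receive pre-medication they do not need: at most 84 − 28 = 56 more than under roll-out at one dose, or 84 − 56 = 28 more than under roll-out at both. The 84 participants, the 30 events in the primary pair, the 45 events overall, and the alpha and power are unchanged.
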